5.4.1 Use of DataCore/Epic Information for Recruitment Purposes

This study will utilize EPIC to identify subjects. A study team member will submit a request to DataCore to identify potential participants. Data points to be searched will include age, diagnosis of prediabetes, HbA1c in the prediabetic range over the previous year provided there is no diagnosis of T2DM or record of taking antidiabetic medication other than metformin (HbA1c: $\geq 5.7\%$ and $<6.5\%$), no diagnosis of bipolar disorder, and active MyChart participation. DataCore queries will be run at the start of the study and monthly after the study starts depending on recruitment rates. DataCore will request a report from EPIC for these patients with identifiable protected health information (name, email address) for research related purposes. Only the PI and project coordinator will have access to the search results. The Epic team will set up an IRB approved recruitment message in MyChart and work with the PI and project

CONFIDENTIAL

This material is the property of the NYU School of Medicine and NYU Langone Health. Do not disclose or use except as authorized in writing by the study sponsor
Behavioral Intervention Template Version: 11 January 2019

coordinator to send it out. The message will include a description of the study, inclusion and exclusion criteria, and contact information for the PI (phone number and email). Participants responding that they are interested in the study will be sent a MyChart message to arrange for a convenient date and time for the telephone screen. The recruitment message may be repeated two times at one-month intervals if needed for subject recruitment (total 3 MyChart messages). These data will be used solely for participant identification in order to determine patients who are initially eligible and for chart review. If any recruitment information does need to be sent by email, the SendSafe Secure email method will be used. The study team will discard information from those who do not wish to participate in the study.

If a subject requests information regarding opting out of further recruitment for all research, subjects will be directed to contact [contact] or [name].

5.5 Duration of Study Participation

Study participants' participation will involve a 3-4 week baseline phase that will include the CTSI visit 1, a 2 week at-home baseline assessment for sleep and glycemic control, using accelerometers (14 nights), continuous glucose monitors (7 days), and pulse oximetry (1 night, if needed). These 2 weeks will be followed by a 1-week review of the at-home data by the PI to assess continued eligibility (e.g., objectively confirmed short sleep). The at-home baseline assessment will be followed by the 8-week intervention. After the 8-week intervention, participants will return to the CTSI for the wrist accelerometer and continuous glucose monitor for the 2-week at-home end of treatment assessment. Thus, participants can anticipate involvement in the study for approximately a 15 week period.

5.6 Total Number of Participants and Sites

This is a single site study being conducted at NYULH. Recruitment will end when approximately 800 participants are enrolled. It is expected that approximately 800 participants will be enrolled in order to produce 188 evaluable participants.

5.7 Participant Withdrawal or Termination

5.7.1 Reasons for Withdrawal or Termination

Participants are free to withdraw from participation in the study at any time upon request. An investigator may terminate participation in the study if:

- Any clinical adverse event (AE), laboratory abnormality, or other medical condition or situation occurs such that continued participation in the study would not be in the best interest of the participant.
- The participant meets an exclusion criterion (either newly developed or not previously recognized) that precludes further study participation.
- At the discretion of the PI for lack of adherence to the intervention or study procedures or visit schedules (e.g., target 80% of weekly daily diary completion and 80% attendance at intervention sessions). Reasons for less adherence will be assessed, and if addressable will be re-evaluated at the next scheduled intervention session.
- The participant does not respond to weekly phone calls/emails for 4 weeks during the intervention.

5.7.2 Handling of Participant Withdrawals or Termination

Participants will be considered withdrawn if they cannot be contacted for 4 weeks during the intervention using all of the contact information collected. No further efforts will be made to contact the participant and that participant will be considered lost to follow-up. Abrupt termination of participation in the study intervention poses no safety risk to participants. As this study is minimal risk, efforts will not be made to collect safety and efficacy data after withdrawal. If a participant withdraws or is withdrawn from the study, no further study visits or procedures will be completed. It will be documented whether or not each subject completes the clinical study.

CONFIDENTIAL

This material is the property of the NYU School of Medicine and NYU Langone Health. Do not disclose or use except as authorized in writing by the study sponsor
Behavioral Intervention Template Version: 11 January 2019

Any data collected before withdrawal from the study will be retained for analysis, and no new data will be collected. If the participant requests that data be destroyed, all paper records will be shredded, and any data already processed into computer files will be removed. However, if results based on the participant's data have been submitted for publication or presentation before the request is made, the results cannot be removed from the publication or presentation.

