5.2 Exclusion Criteria

An individual who meets any of the following criteria will be excluded from participation in this study:

1. Diagnosis of T2DM or taking insulin or oral hypoglycemic medications (other than Metformin or Glucophage). The diagnosis of T2DM and treatment with anti-diabetic agents will confound continuous glucose monitoring assessments. Individuals taking metformin alone will not be excluded as metformin is frequently prescribed for prediabetes.
2. Pregnancy/lactation. Pregnancy and lactation can disrupt habitual sleep patterns and our primary interest is in recruiting individuals with habitual short sleep. Additionally, hormonal changes during pregnancy increase insulin resistance and may confound continuous glucose monitoring results⁹³.
3. Current chemotherapy treatments. Current chemotherapy treatments may contribute to fatigue and alter habitual sleep patterns⁹⁴.
4. Alcohol abuse/dependence may interfere with habitual sleep and limit the individual's ability to adhere to the sleep interventions. Alcohol abuse will be assessed with the Alcohol Use Disorders Identification Test (a measure that has demonstrated good reliability and validity). Individuals with scores > 15 (men) or > 13 (women) will be excluded⁹⁵.
5. Recent or planned night shift work (previous 2 months or during the intervention period) or trans-meridian travel > 1 hour time zone difference during the RECR previous 4 weeks or during the intervention period. Shift work and trans-meridian travel of > 1 hour may disrupt habitual sleep and limit the individual's ability to adhere to the sleep interventions.
6. Sleep disorders (other than OSA discussed above and insomnia symptoms). Specific sleep disorders will be assessed with selected questions from the Sleep Disorders Symptom Checklist-(SDS-CL-25) that screens for narcolepsy in questions 18-20 (summed average score ≥ 3), restless legs syndrome in questions 15-17 (summed average score ≥ 3), and parasomnias in question 23 because these sleep disorders may interfere with the individual's ability to adhere to the sleep intervention.
7. Chronic use of sleep-promoting medications (self-reported) defined as taking a sleep-promoting medication ≥ 3 nights per week. Chronic use of sleep medication may interfere with sleep patterns and limit the participant's ability to take part in the sleep interventions.

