Wearable sensor technology assessments will be as follows: pulse oximeter (baseline for 1 night, as needed); Wrist accelerometer (baseline and end of treatment 24/7 for 14 nights); Continuous glucose monitor (baseline and end of treatment 24/7 for 7 days).

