7.3.5 Withdrawal Visit

If a participant withdraws or is withdrawn from the study, no further study visits or procedures will be completed.

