8.4.4 Reporting of Pregnancy

Pregnant or breastfeeding participants will not be able to participate in the study because pregnancy and lactation can disrupt habitual sleep patterns, and hormonal changes during pregnancy increase insulin resistance⁹³. Female participants of child bearing potential will be asked to use a medically accepted method of birth control while in the study. If participants become pregnant during the course of the study, their data will not be used in the analyses.

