10.3 Analysis Datasets

Primary analyses will be performed within an intent-to-treat (ITT) sample, including all participants that are randomized to either the Sleep Intervention or Control Intervention.

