## **1.2 Analysis Datasets**

Primary analyses were performed within an intent-to-treat (ITT) sample, including all participants that were randomized to either the Sleep Intervention or Control Intervention.

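### The primary analysis is labelled ITT, but the pregnancy rule contradicts that label, and outcomes lost through withdrawal have no stated handling, so the regression defaults to complete cases

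*Protocol*

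**What the plan says.** **Analysis set.** Protocol 10.3: "Primary analyses will be performed within an intent-to-treat (ITT) sample, including all participants that are randomized to either the Sleep Intervention or Control Intervention". SAP 1.2 repeats this in the past tense: "Primary analyses were performed within an intent-to-treat (ITT) sample, including all participants that were randomized to either the Sleep Intervention or Control Intervention".

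**Outcome.** Protocol 10.4.2 and SAP 1.3.2 regress each participant's change from baseline in percent time with glucose at or above 140 mg/dL on arm. Protocol 7.1.1 schedules continuous glucose monitoring (CGM) only at baseline and end of treatment, 7 days each time. Randomisation falls in week 3 and the second recording follows the eight intervention weeks (7.3.3, 7.3.4).

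**After withdrawal.** Protocol 5.7.2: "As this study is minimal risk, efforts will not be made to collect safety and efficacy data after withdrawal". Protocol 7.3.5: "If a participant withdraws or is withdrawn from the study, no further study visits or procedures will be completed". Under 5.7.1 the investigator may also end participation: "At the discretion of the PI for lack of adherence to the intervention or study procedures or visit schedules". That clause adds that the reasons are assessed first and looked at again at the next session if they can be addressed.

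**Pregnancy.** Protocol 8.4.4: "If participants become pregnant during the course of the study, their data will not be used in the analyses". Section 5.2 gives a rationale: "hormonal changes during pregnancy increase insulin resistance and may confound continuous glucose monitoring results".

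**Missing data.** Protocol 10.1 leaves detail to the SAP. Protocol 10.4.1 lists a check for nonrandom missingness, and then names imputation as one remedy for variables that are not normally distributed. SAP 1.3.1 keeps the check and drops the sentence on imputation.

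**The concern.** A result labelled ITT will be read as applying to everyone randomised. Two things stand in the way, and they differ in kind.

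- The pregnancy rule is a post-randomisation exclusion. It removes people from the analysis even when their outcome was measured, and nothing reconciles it with 10.3 or SAP 1.2.
- The withdrawal rules leave the ITT set unchanged but empty the outcome for some of its members. Because low adherence is one permitted reason for withdrawal, the missing outcomes may be related to adherence. The protocol already plans a separate per-protocol analysis (10.4.8). Losing the outcomes of non-adherent participants moves the ITT result towards that analysis.

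An ordinary regression drops records without an outcome. With no stated method, the analysis set is decided by software default. The 20% allowance in Protocol 10.5 protects power. It does not protect against bias from who is lost.

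**Working it through.** **1. The plan's own figures.** Protocol 10.5 assumes 0.6 SD, two-sided alpha 0.05 and 95% power. A noncentral-t calculation gives 74 per arm (power 95.2%), as stated. Rounded up to 75, 75 / (1 - 0.20) = 93.75, so 94 per arm and 188 in total. The sample size reproduces and is not in question.

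**2. How many could lack an outcome.** The Schematic of Study Design has 94 per arm, to retain 75.
- At the planning allowance: 188 - 2 x 75 = 38, or 38/188 = 20.2%.
- At 10% loss: 0.10 x 188 = 18.8, about 19. At 5%: 0.05 x 188 = 9.4, about 9.

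The 38 is the ceiling of the plan's allowance, because the 20% in 10.5 covers loss to follow-up and non-adherence together. A non-adherent participant who is not withdrawn still provides the second recording.

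**3. Effect on the estimate.** Express benefit in SD units. Let p be the fraction lost in each arm (assumed equal), and let g be how much worse lost participants do than completers in that arm. The all-randomised mean in an arm is (1 - p) x completer mean + p x (completer mean - g) = completer mean - p x g. Taking sleep arm minus control arm, with G = g(sleep) - g(control):

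all-randomised difference = complete-case difference - p x G

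G is not in the documents; the range below is an assumption. G = +0.6 would arise, for example, if lost sleep-arm participants changed as controls do and control-arm losses were uninformative. With p = 0.20 and a complete-case effect of 0.60 SD:

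| G (SD) | p x G | Effect in all randomised (SD) |
|---|---|---|
| -0.6 | -0.12 | 0.72 |
| -0.3 | -0.06 | 0.66 |
| 0 | 0 | 0.60 |
| +0.3 | +0.06 | 0.54 |
| +0.6 | +0.12 | 0.48 |

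For G between -0.6 and +0.6, the range narrows to 0.54 to 0.66 SD at 10% loss (0.10 x 0.6 = 0.06) and 0.57 to 0.63 SD at 5% (0.05 x 0.6 = 0.03).

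**4. What would change the conclusion.** With 75 per arm, SE = sqrt(2/75) = 0.163 SD. With t critical 1.976, the significance threshold is 1.976 x 0.163 = 0.323 SD. The gap needed to bring the all-randomised effect down to that threshold is:
- 0.60 SD observed: (0.60 - 0.323) / 0.20 = 1.39 SD.
- 0.40 SD observed: (0.40 - 0.323) / 0.20 = 0.39 SD.

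This uses the complete-case standard error without covariates, so it is approximate.

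**5. Pregnancy.** No count is given. Participation lasts about 15 weeks (5.5), contraception is requested (8.4.4) and ages run from 21 to 64 (5.1), so the number is probably small. That is an inference from the design.

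**The case against.** Several points on the other side stand.

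- **The withdrawal rule does not contradict the ITT definition.** A reader might infer that 5.7.2 and 7.3.5 remove people from the set. They do not: the set says who is counted and in which arm, while those sections leave outcomes missing. Only 8.4.4 contradicts the definition.
- **The plan tries to limit loss.** Section 5.4 plans outreach for missed sessions, 5.7.1 has reasons for low adherence assessed first, and 5.7.2 keeps data collected before withdrawal. But for someone who leaves before the second recording, the retained glucose data are baseline only, so no change score can be formed.
- **Imputation was contemplated.** In Protocol 10.4.1 it closely follows the missing-data check. Even so, it is tied to non-normality, has no model or assumption, and is absent from the SAP.
- **The direction of bias is unknown.** It is tempting to say that complete cases flatter the sleep arm. The documents do not support that: the shift reverses if control-arm losses are the more informative.
- **The total of 188 is mostly consistent.** A reader might infer several conflicting meanings. The Schematic uses retaining in the sense of passing from one screening stage to the next, and the Protocol Summary fits that sense. Only 5.4, which has 188 people finishing the intervention, clearly conflicts with 188 randomised and about 75 per arm retained. The word evaluable in 5.6 is ambiguous.

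**Conclusion.** The point holds and should be fixed. Following 5.7.1, 5.7.2, 7.3.5 and 8.4.4 as written, with no missing-outcome method, yields a complete-case analysis under an ITT label. The pregnancy exclusion is a direct contradiction, probably small in numbers. The withdrawal rules are a missing-outcome problem affecting up to about 38 of 188 at the plan's allowance; the documents do not say how many were or will be lost.

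Under equal 20% loss, the illustrated shift is up to 0.12 SD either way, and zero if losses are equally informative in both arms. The conclusion would be fairly robust if the 0.6 SD design effect were observed and fragile if the effect were nearer 0.40 SD. These figures rest on an assumed gap. They do not show that the estimate is biased.

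**What to change.** 1. **Outcome collection, if follow-up is still open.** Amend Protocol 5.7.2 and 7.3.5 so that stopping the sessions, or not adhering, does not by itself end outcome collection. Invite those who still consent and can be reached to the already scheduled Visit 2 and 7-day recording. Leave out anyone whose participation was ended because continuing was not in their best interest, and leave those withdrawal decisions unchanged. Cost: amendment wording and some staff effort. Participants who withdraw consent or cannot be reached stay missing.
2. **Pregnancy.** Reconcile 8.4.4 with 10.3 and SAP 1.2. Keep these participants in the ITT set as randomised and state a rule for their outcome, for example treating CGM obtained during pregnancy as missing and handling it under item 3.
3. **SAP.** Name a missing-outcome method, for example multiple imputation using arm, baseline percent time at or above 140 mg/dL, age, sex, race and session attendance. State that it assumes missing at random, and add a delta-adjusted sensitivity analysis because that assumption may fail. Report numbers randomised and numbers with an outcome, by arm and reason. Cost: modest analysis work.
4. **Counts.** Correct 5.4 to agree with 188 randomised and about 75 per arm retained (Schematic, 10.5), and define evaluable in 5.6.

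The SAP's mostly past tense suggests that the analysis may already be done. Item 1 would then no longer be possible. Additions under items 2 and 3 should be labelled post hoc or, if they are not made, the primary set should be described as complete cases rather than ITT.

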8.3 Time Period and Frequency for Event Assessment and Follow-Up

The occurrence of an AE or SAE may come to the attention of study personnel during study visits and interviews of a study participant presenting for medical care, or upon review by a study monitor. All AEs including local and systemic reactions not meeting the criteria for SAEs will be captured on the

CONFIDENTIAL

This material is the property of the NYU School of Medicine and NYU Langone Health. Do not disclose or use except as authorized in writing by the study sponsor
Behavioral Intervention Template Version: 11 January 2019

appropriate RF. Information to be collected includes event description, time of onset, clinician's assessment of severity, relationship to study intervention (assessed only by those with the training and authority to make a diagnosis), and time of resolution/stabilization of the event. All AEs occurring while on study must be documented appropriately regardless of relationship. All AEs will be followed to adequate resolution.

Any medical condition that is present at the time that the participant is screened will be considered as baseline and not reported as an AE. However, if the study participant's condition deteriorates at any time during the study, it will be recorded as an AE. UPs will be recorded in the data collection system throughout the study.

Changes in the severity of an AE will be documented to allow an assessment of the duration of the event at each level of severity to be performed. AEs characterized as intermittent require documentation of onset and duration of each episode.

The PI will record all reportable events with start dates occurring any time after informed consent is obtained until 7 (for non-serious AEs) or 30 days (for SAEs) after the last day of study participation. At each study visit, the investigator will inquire about the occurrence of AE/SAEs since the last visit. Events will be followed for outcome information until resolution or stabilization.

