All unresolved adverse events should be followed by the investigator until the events are resolved, the subject is lost to follow-up, or the adverse event is otherwise explained. At the last scheduled visit, the investigator should instruct each subject to report any subsequent event(s) that the subject, or the subject's personal physician, believes might reasonably be related to participation in this study. The investigator should notify the study sponsor of any death or adverse event occurring at any time after a subject has discontinued or terminated study participation that may reasonably be related to this study.

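### Section 5.7.2 stops safety data collection at withdrawal, while sections 8.3 and 8.5 require it to continue, so for withdrawn participants who can still be reached the site cannot follow both

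*Protocol*

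**What the plan says.** Two parts of the protocol govern what happens to safety data once someone leaves.

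**Withdrawal sections.** Section 5.7.2 states: "As this study is minimal risk, efforts will not be made to collect safety and efficacy data after withdrawal". It adds: "Any data collected before withdrawal from the study will be retained for analysis, and no new data will be collected". Section 7.3.5 states: "If a participant withdraws or is withdrawn from the study, no further study visits or procedures will be completed". Section 5.7.1 makes an AE one of the grounds on which the investigator may end participation: "Any clinical adverse event (AE), laboratory abnormality, or other medical condition or situation occurs such that continued participation" is no longer in the person's interest.

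**Safety sections.** Section 8.3 states: "All AEs will be followed to adequate resolution". It records reportable events from consent "until 7 (for non-serious AEs) or 30 days (for SAEs) after the last day of study participation". It then says: "All unresolved adverse events should be followed by the investigator until the events are resolved, the subject is lost to follow-up", or the event is explained in some other way. It also asks for changes in severity to be documented, and for the sponsor to be told of deaths or AEs after discontinuation that may be related to the study. Section 8.5 has serious AEs (SAEs) followed until they resolve satisfactorily or are judged chronic or stable.

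Section 8 names loss to follow-up as an end to follow-up. It does not name withdrawal.

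**The concern.** Both sets of instructions are current and apply to the same people. A participant whom the investigator withdraws because of an AE may have that AE still open and may be perfectly willing to answer a call. Section 8.3 tells staff to follow the event and record new ones for a fixed period. Section 5.7.2 tells them to make no effort to do so.

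At stake is the completeness of the AE record in the group where AE-related exits occur: how long an event lasted, whether it worsened, how it ended, and whether anything new began shortly after exit. That record feeds the monthly medical-monitor review (section 8.8) and the annual report to the IRB (section 8.4.1). If the choice is left to staff, follow-up may also differ from one withdrawn participant to the next.

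**Working it through.** The contradiction is one of wording, so the main check sets the sections side by side for each type of participant. Arithmetic serves only to bound the number of people.

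**1. Who falls under which rule**

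- *Reachable, withdrawn, AE open.* Section 5.7.2: no safety collection. Sections 8.3 and 8.5: follow until resolved (for SAEs, also until judged chronic or stable). Direct conflict.
- *Reachable, withdrawn, no AE open.* Section 5.7.2: no new data. Section 8.3: record new events for 7 or 30 days. Direct conflict.
- *Unreachable for 4 weeks during the intervention.* Section 5.7.2 classes the person as lost to follow-up, and section 8.3 ends AE follow-up at that point. Little conflict.
- *AE reported before withdrawal.* Recorded on study under sections 7.3.3, 8.3 and 8.4.1, and kept under section 5.7.2 unless the participant asks for the data to be destroyed. No conflict over the fact of the event, only over its later course.

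**2. What the windows cover**

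Assume that the day of withdrawal counts as the last day of participation. For withdrawal on day *d*, section 8.3 records non-serious AEs to day *d* + 7 and SAEs to day *d* + 30. As an illustration, withdrawal on day 35 gives 35 + 7 = day 42 and 35 + 30 = day 65. Under section 5.7.2 neither window would be actively collected.

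**3. How many people**

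Inputs from section 10.5 and the study schematic: 75 per arm to be retained, up to 20% loss or non-adherence, 94 per arm randomised.

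- The plan's own figure: 75 / (1 − 0.20) = 93.75, rounded up to 94 per arm; 2 × 94 = 188. This reproduces exactly.
- Planned loss: 94 − 75 = 19 per arm; 2 × 19 = 38; 38 / 188 = 20.2%.

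The 38 is a ceiling by the plan's own allowance. It includes non-adherent people who may never be withdrawn and unreachable people whom section 8.3 excepts. The documents give no split, so the number in direct conflict could lie anywhere from 0 to about 38 of those randomised. Withdrawals between consent and randomisation would be extra, because section 8.3 starts recording at consent; no figure is given for them.

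**4. Effect on the statistics**

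The 188 and its power rest on the glucose endpoint and the 20% allowance. Neither depends on which safety rule is followed.

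**The case against.** The strongest defence is that the study is minimal risk, that section 5.7.2 gives this as its reason, and that the dedicated safety section would govern in practice. It does not settle the matter. Section 8 was written for the same minimal-risk study and still sets the duties, and no text says which section prevails. Section 2.3.1 also lists insomnia, sleepiness and infection at the sensor site, which could outlast a withdrawal.

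The defence does limit the point. A reader might infer several stronger things that the documents do not support:

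- *That harms which cause withdrawal are lost.* An AE that leads the investigator to end participation is known beforehand, recordable on study, and kept. Its later course is what is exposed. A harm could be missed entirely only if it was never reported before the person left.
- *That section 7.3.5 ends all contact.* It ends visits and procedures. The stop on safety data comes from 5.7.2, and the stop on contact attempts in 5.7.2 concerns people already unreachable.
- *That the comparison of harms between arms is biased toward no harm.* Section 10.4.4 plans no such comparison, nor do the SAP sections available. Nothing shows that withdrawal would be higher in the sleep arm.
- *That all 38 people lose 30 days of safety data.* The figure is a mixed ceiling, as shown above.
- *That completers have the same defect.* No contact is scheduled during their 30-day window, but no section forbids collecting those events, and section 8.4.1 encourages participants to report any AE at once. An active contact at the end of that window would be a preference, not the repair of a contradiction.

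**Conclusion.** The contradiction stands. For withdrawn participants who can be reached, section 5.7.2 cannot be obeyed together with sections 8.3 and 8.5. The consequence is limited: outcome, duration or worsening of open AEs, and new events in the 7- and 30-day windows, may go unrecorded.

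The size is unknown, from 0 to about 38 of 188 randomised, plus any withdrawals before randomisation. This rests on two assumptions: that the day of withdrawal is the last day of participation, and that losses stay within the planned 20%. The conclusion that the sections conflict needs neither. The point should be corrected because it concerns the safety record, but it does not touch the primary result.

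**What to change.** Reconcile the passages. Amend section 5.7.2, and cross-reference it in 7.3.5, so that withdrawal ends the intervention, study visits and efficacy collection, while safety data collection continues as section 8.3 already sets out: open AEs followed, and new events recorded through the 7- and 30-day windows. Do this by remote contact, and stop if the participant refuses further contact or is lost to follow-up. No new window is needed, since the periods are already in the protocol.

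The cost is a wording change and a small amount of coordinator time, using the telephone, email and REDCap routes already in place. No extra visit is required. If follow-up has already finished, the report should say which rule the site applied and how many withdrawn participants had an AE open at exit.
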